### **Subject stratification**

As noted above, subjects will be stratified into 3 groups based on their degree of insulin resistance, as defined by their glucose disposal rate (GDR) measured via hyperinsulinemic/euglycemic clamp during the experiment.

- 1) ***“Insulin resistant” [IR]*** (GDR  $< 28 \mu\text{mol/kg fat free mass [FFM]/min}$ ),
- 2) ***“Mildly insulin resistant” [MIR]*** (GDR  $> 28 \mu\text{mol/kg FFM/min}$  and  $< 40 \mu\text{mol/kg FFM/min}$ )
- 3) ***“Non-insulin resistant” [NIR]*** (GDR  $> 40 \mu\text{mol/kg FFM/min}$ ).

The “cutoff points” used to stratify our subjects into these 3 groups were defined by Stern et al., (25). Stern, et al., used a statistical approach using hyperinsulinemic-euglycemic clamp data from 2,138 ethnically diverse non-diabetic subjects (insulin infusion rate =  $40 \text{ mU/m}^2/\text{min}$ , which is the same as we propose here). They defined the “optimal insulin resistance cutoff” as being  $< 28 \mu\text{mol/kg FFM/min}$ . We will make every effort to closely balance subject characteristics across the three study groups (including sex).

### **Primary phenotype measurements for Specific Aim #1**

During the clinical study outlined above, we will perform several clinical and sub-clinical assessments to help characterize our subject population.

**Insulin resistance** will be assessed during the hyperinsulinemic-euglycemic clamp. The primary measure of insulin resistance will be calculated as the steady-state rate of glucose infusion (GDR) during the 20 min period at the end of the clamp. We will also assess hepatic insulin resistance (i.e., magnitude of reduction in hepatic glucose production (HGP) in response to insulin) using stable isotope tracer methods, and peripheral tissue insulin resistance (i.e., difference between whole-body GDR and HGP). Detailed methods for this procedure, including methods used to quantify the tracer-tracee ratio (TTR) for  $d_2$ -glucose using gas chromatography/mass spectrometry (GC/MS) can be found in our recent publication (16).

**In vivo rates of lipolysis and fatty acid mobilization in the systemic circulation** We will measure TTR for  $d_5$ -glycerol and  $^{13}\text{C}$ -palmitate using the same GC/MS analysis methods we have used previously in many of our studies (4, 17, 21, 22, 26).

**Resting energy expenditure and fat oxidation rate** will be measured using indirect calorimetry (7).

**Plasma substrates and hormone concentrations**. Plasma concentrations of triglyceride, fatty acid, glucose and insulin will be assessed using commercially available assays kits (Sigma, Wako, and ThermoDMA, Millipore, respectively). Plasma epinephrine and norepinephrine will be measured by HPLC with electrochemical detection by the pathology lab at the University of Michigan Medical Center.

**Blood lipid profile**. Plasma concentrations of total- and high-density lipoprotein cholesterol (Total-C and HDL-C) will be measured using commercially available colorimetric assay kits; Cholesterol E and HDL-Cholesterol E; WAKO Life Sciences, Inc.) and plasma low-density lipoprotein (LDL) cholesterol will be calculated as:  $[\text{LDL-C}] = [\text{Total-C}] - [\text{HDL-C}] - [\text{Triglyceride}]/5$ .

**Body composition and visceral adiposity**. Percent body fat will be assessed using a Dual Energy X-ray Absorptiometry [DEXA: Lunar DPX, DEXA Scanner]. We also plan to measure hepatic fibrosis, the amount of fat stored in the liver and visceral fat (or intra-abdominal fat) using magnetic resonance imager (MRI) with elastography as described previously (1).

**Liver function**. Circulating markers of liver function will be assessed in serum.

**Quantifying factors regulating triglyceride storage and adipogenic markers**.

Isolation of adipocytes and stromal vascular fraction (SVF) will be performed by collagenase digestion and centrifugation methods on fresh adipose tissue biopsy samples as previously described (3, 24). Immunoblot analysis to quantify protein abundance of enzymes and other co-factors regulating lipolysis and fatty acid esterification will be performed on the purified adipocyte fraction (13, 17). We will quantify the abundance of key adipogenic markers in the SVF. Table 1 provides a list of some of the proteins we plan to measure. We also plan to measure mRNA expression of many of these factors using the StepOnePlus real time PCR system (Life Technologies) with fluorescent probe-based assays (IDT).

**Table 1.** Adipose proteins to measure

	LIPOLYSIS	TRIGLYCERIDE SYNTHESIS	ADIPOGENIC MARKERS
Proteins of interest	ATGL, CGI-58, HSL, caveolin, p-HSL-s565, 563, 660, Perilipin-1	DGAT, mGPAT, AGPAT-1, PAP (LIPIN-1), SCD-1, SREBP-1c	PPAR $\gamma$ , C/EBP $\alpha$ , b, g, FABP4, Chemerin, Adiponectin, FAS

Lipolytic activity in adipose tissue explants and cultured cells (basal, stimulated and insulin inhibited). Lipolytic experiments will be performed on fresh adipose tissue samples *ex vivo* (~50mg; cultured at 5% CO2 in Krebs buffer + 2.5% BSA (pH 7.4)), as well as in primary cells differentiated from adipose stromal vascular cells (aSVC) derived from these adipose tissue biopsy samples. Lipolysis will be assessed in optimally differentiated aSVC (12). The differentiated cells will be washed, serum-starved for 4 hours, and incubated in basal [1 U/mL adenosine deaminase + 20 nM N6-(L-2-phenylisopropyl)-adenosine], stimulated (1 mM 8-bromo-cAMP), or stimulated + insulin (30 pM, 120 pM, or 600 pM insulin) conditions for 2 hours. Importantly, by performing these experiments on fresh tissue and aSVC, we will examine the lipolytic action of existing mature adipocytes, as well as the innate lipolytic action of derived pre-adipocytes.

Esterification activity in adipose tissue samples. We will measure basal GPAT and DGAT activity in adipose tissue lysate samples using C-G3P and C-palmitoyl-CoA, as we have reported previously (17, 23).

Adipogenic capacity assays (in vitro). Adipose stromal vascular cells (aSVC) will be derived from fresh adipose tissue samples as described above. Subcultured aSVC from individual subjects will be plated on 24-well plates. When confluent, cells will be incubated for 7 days in either: 1) optimal differentiation media (+IBMX and +TZD; (12)), 2) suboptimal differentiation media (optimal media without IBMX and TZD), or 3) control media (containing 15% FBS). Incubation in the suboptimal media will provide information regarding whether the aSVCs from the different subject groups are already primed for differentiation, while the optimal media will allow us to compare the maximum capacity of the aSVCs to differentiate. After 7 days of incubation in these different media, cells will incubate in a maintenance medium (12). Ten days after the induction of differentiation, cells will be harvested for qPCR analysis of *PPARG* and *FABP4* gene expression levels.

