Although we contend that alterations in adipose tissue structure and metabolic function play a key role in determining insulin resistance in obesity, other factors obviously contribute as well. For example, because skeletal muscle is the predominant site of insulin-mediated glucose uptake, abnormalities in insulin signaling events within skeletal muscle also underlie systemic insulin resistance. Protein tyrosine phosphorylation (pTyr) plays critical role regulating key biological processes, including insulin signaling. Using state-of-the-art mass spectrometry-based proteomics, we can quantify hundreds of pTyr sites simultaneously, and by doing so we anticipate discovering novel pTyr targets that may differentiate insulin sensitive vs. insulin resistant obese adults. These findings will help identify new molecular mechanisms underlying insulin resistance, and will provide novel targets for preventing and treating type 2 diabetes and other obesity-related diseases.

In this project, we will measure insulin-mediated glucose uptake in a homogeneous cohort of abdominally obese adults, and then stratify them into three distinct groups based on their degree of insulin resistance. Our main comparisons will be made between the most- and least-insulin resistant groups.

**SPECIFIC AIM #1:** *Compare factors regulating triglyceride storage and adipogenesis in subcutaneous adipose tissue from insulin-sensitive obese adults compared with a well-matched cohort of insulin resistant subjects.*

**Hypothesis 1:** Compared with adipose tissue from obese adults who are insulin resistant, adipose tissue from those who remain relatively insulin sensitive will have: a) lower abundance and basal activity of lipolytic enzymes b) higher abundance and basal activity of esterification enzymes, c) greater anti-lipolytic response to insulin (measured *in vivo* and *in vitro*), d) greater expression of adipogenic markers (e.g., PPAR $\gamma$  and C/EBP $\alpha$ ), e) elevated adipogenic capacity (measured *in vitro*), f) higher adipocyte cell density (cells/cm $^2$ ), g) greater angiogenic capacity (measured *ex vivo*), and h) less adipose tissue fibrosis.

**SPECIFIC AIM #2:** *Identify other important and novel factors that contribute to the protection against insulin resistance in some obese adults.*

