## Detailed clinical study procedures

Subjects will complete a physical activity questionnaire and a three day food journal before their hospital visit. On the morning of the study, subjects will be admitted to the Michigan Clinical Research Unit (MCRU) at 0700h. Subjects will arrive at the Michigan Clinical Research Unit (MCRU) in the University of Michigan Medical Center in the morning after an overnight fast. After arrival, subjects will rest quietly in their room for 30 min. We will then measure their resting metabolic rate (RMR) using a canopy-equipped metabolic cart (Vmax metabolic cart; Viysis, Inc.) for 20min. After RMR measurement, intravenous catheters (IVs) will then be placed in a forearm or hand vein of both arms. Approximately 1.5h after admission to the MCRU, we will begin primed, stable isotope infusions of [6,6 d2]glucose (to assess the rates of hepatic glucose production and systemic glucose uptake) and [d5]glycerol (to assess whole body lipolytic rate). At the same time we begin the tracer infusions, we will collect skeletal muscle (vastus lateralis) and subcutaneous abdominal adipose tissue biopsy samples. Approximately 2.5h after admission we will begin an infusion of [C]palmitate (to assess the rate of systemic fatty acid mobilization). Three blood samples will be collected in five minute intervals starting ~50min after beginning the [C]palmitate infusion. Immediately, after collection of these blood samples we will begin a hyperinsulinemic-euglycemic clamp (insulin infusion rate = 40 mU/m^2/min) to assess insulin resistance, as described previously by Defronzo, et al. (6). During the clamp procedure we will collect small blood samples every 5 minutes to assess blood glucose concentration and the glucose infusion rate will be adjusted as necessary to maintain euglycemia, as described previously (6). Thirty minutes after starting the hyperinsulinemic-euglycemic clamp procedure we will collect another skeletal muscle and adipose tissue biopsy samples to acquire a sample in the insulin stimulated condition. Finally, we will collect 5 blood samples during the final 20 minutes of the clamp. Detailed descriptions of these procedures can be found in our previous publications (8, 9, 16, 23), and blood sampling timeline is provided in Appendix 1 of this document.

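### Peripheral insulin resistance is defined as infusion rate minus an unspecified HGP; on either plain reading, incomplete hepatic suppression generally leaks into the peripheral score

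*Combined protocol and SAP*

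**What the plan says.** The insulin-resistance paragraph under Primary phenotype measurements for Specific Aim #1 sets out three quantities.

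- The primary measure is "calculated as the steady-state rate of glucose infusion (GDR) during the 20 min period at the end of the clamp". GDR is thus, by the plan's own definition, an infusion rate.
- Hepatic insulin resistance is the "magnitude of reduction in hepatic glucose production (HGP) in response to insulin", so it needs a basal and a clamp value of HGP.
- The third measure is "peripheral tissue insulin resistance (i.e., difference between whole-body GDR and HGP". No condition (basal, clamp, or the change between them) is attached to HGP.

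The paragraph then sends the reader to a cited publication, reference 16: "Detailed methods for this procedure, including methods used to quantify the tracer-tracee ratio (TTR" and so on. Detailed clinical study procedures assigns the deuterated glucose tracer "to assess the rates of hepatic glucose production and systemic glucose uptake". That section and Appendix 1 schedule three samples just before the clamp and five in its final 20 minutes.

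**The concern.** The infusion rate already falls short of whole-body disposal by whatever glucose the liver still releases during the clamp. Recovering disposal means adding that release back; the plan describes a difference. A subject whose liver responds poorly to insulin could then look peripherally resistant with entirely normal peripheral uptake.

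The purpose of the paragraph is to separate hepatic from peripheral resistance. If hepatic suppression differs between the IR and NIR groups, a score that mixes the two would attribute part of a hepatic difference to peripheral tissue.

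**Working it through.** The plan gives no numerical value for HGP or for peripheral insulin resistance, so there is no figure to reproduce. The check is steady-state mass balance.

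**Inputs from the plan.** GDR = GIR over the final 20 min of the clamp; peripheral measure = GDR − HGP, condition unstated; group cutoffs of 28 and 40 µmol/kg FFM/min (Subject stratification), used below only as example infusion rates.

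**Assumed inputs.** All HGP and Rd values below are assumptions for illustration. Units are µmol/kg FFM/min.

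**Step 1: identities.**
- Rd_clamp = GIR + HGP_clamp
- Rd_basal = HGP_basal
- Rise = Rd_clamp − Rd_basal = GIR − (HGP_basal − HGP_clamp)

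**Step 2: the three readings, with GDR = GIR.**
- Minus clamp HGP: GIR − HGP_clamp = Rd_clamp − 2 × HGP_clamp
- Minus basal HGP: GIR − HGP_basal = (Rd_clamp − Rd_basal) − HGP_clamp
- Minus the reduction: GIR − (HGP_basal − HGP_clamp) = Rd_clamp − Rd_basal

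Only the third is free of a residual hepatic term in general. It measures the rise, not total uptake. No version that subtracts HGP from GIR gives total uptake unless clamp HGP is zero.

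**Step 3: two subjects with the same periphery.** Assume Rd_clamp = 30 and HGP_basal = 12 in both, with HGP_clamp 1 in subject A and 5 in subject B. Then GIR = 30 − 1 = 29 and 30 − 5 = 25.

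| Reading | A | B | Difference (truth 0) |
|---|---|---|---|
| GIR − clamp HGP | 29 − 1 = 28 | 25 − 5 = 20 | 8 |
| GIR − basal HGP | 29 − 12 = 17 | 25 − 12 = 13 | 4 |
| GIR − reduction | 29 − 11 = 18 | 25 − 7 = 18 | 0 |

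**Step 4: a group contrast.** Assume GIR 40 (NIR) and 28 (IR), basal HGP 15 in both, and suppression of 90% and 60%. Clamp HGP is 1.5 and 6; Rd_clamp is 41.5 and 34. The true gap is 7.5, whether measured as Rd or as the rise, because basal HGP is equal.
- Clamp reading: 38.5 − 22 = 16.5
- Basal reading: 25 − 13 = 12.0
- Reduction reading: 26.5 − 19 = 7.5

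If suppression is 75% in both groups instead (clamp HGP 3.75 in each), all three readings and the truth give 12.0.

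**Step 5: range for one subject.** With basal HGP assumed at 12 to 18 and suppression at 50% to 100%, clamp HGP runs from 0 to 18 × 0.5 = 9. The basal reading then falls below the rise by 0 to 9. The clamp reading falls below total Rd by 0 to 18.

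**Step 6: the target matters.** Assume NIR and IR values of Rd_clamp 45 and 30, clamp HGP 2 in both, and basal HGP 12 and 15. GIR is 43 and 28. The gap in Rd is 15; the gap in the rise is 33 − 15 = 18. The clamp reading gives 41 − 26 = 15, correct for Rd and 3 too small for the rise. The reduction reading gives 33 − 15 = 18, correct for the rise and 3 too large for Rd. No error can be stated until the plan says which quantity it wants.

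**The case against.** The disputed words are a short gloss, not an equation, and the method is deferred to a publication that was not available for this check. That publication may give a correct calculation. A reader might infer that the trial will compute peripheral resistance wrongly; the documents do not support that. They show that the stated rule is incomplete and, read plainly, wrong.

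The sentence also introduces HGP inside the phrase on its reduction. Carrying that quantity forward gives the valid third reading. This is possible, but the sentence reserves the reduction for the hepatic measure and then subtracts HGP without qualification, so an analyst cannot be relied on to read it that way.

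Whole-body GDR might be taken to mean tracer-derived Rd. Then subtracting basal HGP gives the rise, but subtracting clamp HGP merely returns GIR. The ambiguity remains, and the paragraph's own definition of GDR points away from this reading.

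The leak is not universal. With complete suppression, the clamp reading equals total Rd and the basal reading equals the rise. At exactly 50% suppression, the clamp reading happens to equal the rise. These limits stand.

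Finally, a reader might infer that the grouping is at fault, since the background says "we will measure insulin-mediated glucose uptake in a homogeneous cohort of abdominally obese adults, and then stratify them into three distinct groups" and Subject stratification describes groups "as defined by their glucose disposal rate (GDR) measured via hyperinsulinemic/euglycemic clamp during the experiment". The documents do not support this as a consequence of the point. Stratification uses the same acronym that the measurement section defines operationally as the infusion rate, and the subtraction of HGP plays no part in it.

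**Conclusion.** The point holds as a minor definitional error. Given GDR as the infusion rate, both plain readings of the peripheral measure generally carry residual hepatic output into the score when suppression is incomplete. The algebra rests on steady state in the sampling windows and on no assumed HGP value.

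The size in this trial is unknown. The errors above follow from assumed inputs. With basal HGP equal between groups, the group-level error vanishes when mean clamp HGP is also equal. Hypothesis 2A expects less hepatic lipid in insulin-sensitive subjects, which is a reason not to presume equal hepatic suppression, but it supplies no figure.

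The effect is confined to a secondary phenotype measure. It appears in none of Hypotheses 1, 2A or 2B, is not named under Statistical analysis, and is in neither Table 2 nor Table 3. Under the plan's definition of GDR, the primary insulin-resistance measure, the three groups and the sample sizes are unaffected.

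**What to change.** Replace the gloss in the insulin-resistance paragraph with one equation, choosing the target explicitly:

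- total peripheral glucose uptake: tracer-derived Rd over the final 20 min of the clamp = GIR + HGP_clamp, per kg FFM; or
- if the increment is intended: Rd_clamp − Rd_basal = GIR − (HGP_basal − HGP_clamp), per kg FFM.

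Label GIR and Rd as separate quantities, and name the sampling window for each HGP term. If reference 16 already uses one of these equations, state it in the plan.

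The cost is one equation and two labels. The tracer and the samples before and at the end of the clamp are already planned, so no procedure, sample or subject is added.

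### Phospho-HSL is assigned to collagenase-isolated adipocytes with no written step to preserve phosphorylation, so it cannot be assumed to show the in vivo state at biopsy

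*Combined protocol and SAP*

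**What the plan says.** All references are to the combined protocol and SAP.

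- **Isolation.** Primary phenotype measurements for Specific Aim #1, in the paragraph that introduces Table 1: "Isolation of adipocytes and stromal vascular fraction (SVF) will be performed by collagenase digestion and centrifugation methods on fresh adipose tissue biopsy samples".
- **Material blotted.** The same paragraph says that immunoblots for enzymes and co-factors "regulating lipolysis and fatty acid esterification will be performed on the purified adipocyte fraction".
- **Panel.** The lipolysis column of Table 1 includes "p-HSL-s565, 563, 660" alongside total proteins. The text presents the table as a partial list.
- **Hypothesis served.** Hypothesis 1a expects "lower abundance and basal activity of lipolytic enzymes" in the insulin-sensitive group.
- **Biopsy timing.** Detailed clinical study procedures has a basal biopsy: "At the same time we begin the tracer infusions, we will collect skeletal muscle (vastus lateralis) and subcutaneous abdominal adipose tissue biopsy samples". A second is taken 30 minutes into the clamp "to acquire a sample in the insulin stimulated condition".
- **Handling after biopsy.** The Skeletal Muscle Biopsy Procedure rinses the sample and places it in liquid nitrogen. The Subcutaneous Adipose Biopsy Procedure puts the core in a vial that typically holds formalin, and passes the aspirate to the assistant for cleaning and processing. It contains no freezing step.
- **Whole-tissue lysate.** This is named as the material for GPAT and DGAT activity, not for the lipolysis blots.

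**The concern.** Total protein abundance and phosphorylation do not have the same stability. The amount of HSL in a cell is not expected to change much during isolation. The fraction phosphorylated at a given site is a balance between kinase and phosphatase activity, and it can shift once living cells leave the circulation and are enzymatically digested and spun. A method suited to abundance is therefore being applied to a marker of state.

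Two consequences are possible. A true NIR v IR difference in phosphorylation could be attenuated and missed. Alternatively, if cells from the two groups respond differently to digestion, that response could be reported as a difference in vivo. A larger sample would not cure the second problem.

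The three HSL sites are the only phosphorylated forms named in Table 1, so they are the listed blot targets that speak to enzyme state rather than enzyme amount. That links them mainly to the activity part of Hypothesis 1a.

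**Working it through.** **Step 1: trace the sample.** Fresh adipose biopsy, then collagenase digestion and centrifugation, then the purified adipocyte fraction, then immunoblot of the lipolysis panel, which includes p-HSL. Each link is stated in Primary phenotype measurements for Specific Aim #1 and Table 1. No other method or material for p-HSL is given.

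**Step 2: look for a preserving step.**

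| Tissue | Written handling | Freezing step written? |
|---|---|---|
| Muscle | Rinsed, vial, liquid nitrogen | Yes |
| Adipose core | Rinsed, vial, typically formalin | No |
| Adipose aspirate | Absorbent pad, cleaned and processed | No |
| Adipose for GPAT/DGAT | Whole-tissue lysate | Storage not described |

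No phosphatase inhibitor or time limit is stated for the adipose blots.

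**Step 3: can the loss be sized?** It would need the processing time t and the turnover half-life h of the sites. The documents give neither. Under a simple decay model the surviving fraction of the contrast is f = 2^(−t/h). All values of t and h below are assumptions:

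- t = 30 min, h = 10 min: 2^(−3) = 12.5%
- t = 60 min, h = 10 min: 2^(−6) = 1.6%
- t = 30 min, h = 2 min: 2^(−15), below 0.1%
- t = 30 min, h = 30 min: 2^(−1) = 50%

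The answer runs from almost nothing to one half according to what is assumed. The model also supposes that the whole group contrast decays to zero, although differences intrinsic to the cells could persist after isolation. No single figure is defensible.

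**Step 4: what attenuation would do to power (illustration only).** The plan gives no sample-size figure for p-HSL. Its governing figure is at least 17 per group, from the rows of Tables 2 and 3 where the expected difference equals the SD, for example 20%/20%, so d = 1.0.

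- Reproduction by normal approximation: n = 2(1.96 + 0.8416)²/d² = 2 × 7.849/1 = 15.7, so 16. The two-sided t-test (noncentral t) gives 17, which matches, with power 0.81.
- Now assume a true d of 1.0 for p-HSL, of which a fraction f survives. The same t-test gives:

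| f | Power with 17 per group | n per group for 80% power |
|---|---|---|
| 1.00 | 0.81 | 17 |
| 0.75 | 0.56 | 29 |
| 0.50 | 0.29 | 64 |
| 0.25 | 0.11 | 253 |

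Both d and f are assumed here. The table shows only that a moderate loss would be enough to make a null p-HSL result uninformative.

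**Step 5: what is not touched.** The lipolysis and triglyceride-synthesis proteins listed as total protein do not depend on a preserved phosphorylation state. Hypothesis 1c is specified as in vivo and in vitro. It is served by the tracer measures and by lipolysis assays in explants and differentiated cells under basal, stimulated and insulin-inhibited conditions. None of these uses p-HSL.

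**The case against.** The best reply is that the plan refers the isolation and blotting to cited methods that are not reproduced in it. Digestion time, temperature, buffer and inhibitors are therefore unknown. The adipose SOP describes the biopsy procedure and stops at processing by the assistant, so a frozen aliquot may exist in practice; GPAT and DGAT lysate shows that undigested tissue is already set aside. Purified adipocytes also give cell specificity that whole tissue lacks. And p-HSL is not among the endpoints in Tables 2 and 3.

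Much of this stands, and it rules out three stronger readings that a reader might infer:

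- **That post-digestion p-HSL simply measures the digestion, or that only about one eighth of the signal can remain.** One eighth is the 12.5% case in the working and rests wholly on an assumed time and half-life.
- **That the plan destroys its own insulin-stimulated readout.** The clamp biopsy is taken for that condition, but the plan never says that the Table 1 blots use it.
- **That Hypothesis 1c is undermined.** Its stated measures do not rely on p-HSL.

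What the reply does not remove is the stated choice of material. The plan does not merely omit a detail: it names the digested, purified fraction for the panel that contains p-HSL, and names lysate for a different assay. Possible good practice that is not written down does not alter that.

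**Conclusion.** The concern holds in a limited form. As written, p-HSL at three sites is measured in adipocytes purified by collagenase digestion, with no described protection of phosphorylation, and so cannot be assumed to represent the in vivo state at biopsy. A group difference could be attenuated or could be partly an effect of processing.

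The size is unknown; the documents supply no inputs from which to derive it. The conclusion rests on one general premise, that phosphorylation is rapidly reversible in living cells. The plan's own timing fits that premise, since it expects an insulin-stimulated tissue state 30 minutes into the clamp, but this does not give the rate at which the sites would change during processing.

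The scope is one supporting marker, mainly for Hypothesis 1a. Total-protein results and the tracer, explant and cell measures stand. The change is worth making before samples are collected, because a phosphorylation state that has been lost cannot be recovered later.

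**What to change.** - **Primary phenotype measurements for Specific Aim #1:** state that p-HSL, with total HSL as denominator, will be measured in whole-tissue lysate from an adipose aliquot frozen in liquid nitrogen immediately after rinsing. Keep the purified adipocyte fraction for total protein abundance.
- **Subcutaneous Adipose Biopsy Procedure:** add the aliquot and freezing step, as the muscle procedure already has.
- **Clamp biopsy:** state which biopsy supplies p-HSL. If it is to be read at 30 minutes of the clamp, handle that sample in the same way.

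The cost is a line in the SOP and a small portion of tissue already being collected; no new biopsy is needed. The downsides are slightly less tissue for digestion and some non-adipocyte protein in the lysate. Using total HSL as denominator expresses phosphorylation relative to the HSL present, but the lysate is still less cell-specific than purified adipocytes, and the plan should say so. If an aliquot is already frozen in practice, the change is only to write it down.
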